5. STUDY INTERVENTIONS

5.1. INTERVENTIONS, ADMINISTRATION, AND DURATION

Participants will be randomized to either Montelukast or placebo in a 1:1 fashion. All participants will be initiated on 10 mg. The dose will be increased in 2-week increments to 20 mg and 40 mg as long as participants report no intolerable symptoms or adverse events (e.g. jaundice, headache, GI symptoms, and neuropsychiatric changes), and liver enzymes checked at 6 weeks do not exceed 3X baseline levels. If participant had positive LFT change (3x increase), dose will be decreased to the prior level (20 mg or matched placebo) and LFT rechecked 2 weeks later. If LFT increases further, then dose will be decreased to 10 mg or matched placebo. If LFT are still increased 2 weeks after 10 mg or matched placebo, study medication will be discontinued. Treatment will be provided in similar capsules format to be taken orally 1-2 times a day. Investigators, study personnel and participants will be blinded for drug assignment. Participants will be treated for 1 year.

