4.2. EXCLUSION CRITERIA

- (1) Intolerance to Montelukast;
- (2) Current diagnosis of bronchial asthma or exercise-induced bronchospasm **and** currently on Montelukast or other leukotriene receptor antagonists (Zafirlukast, Pranlukast);
- (3) Liver disease (elevated liver enzymes ($>2x$ normal): ALT, AST, alkaline phosphatase, total bilirubin);
- (4) Renal disease (Creatinine >2.0 mg/dl), platelets<50,000/ μ l, or INR>1.9;
- (5) Diagnosis of any neurological or psychiatric disorders that affects cognition such as uncontrolled depression, schizophrenia, Parkinson's disease or use of anti-Parkinsonian therapies (unless used for essential tremor), multiple sclerosis, or other active medical condition that in the judgment of the study physicians would affect the safety of the subject or scientific integrity of the study;
- (6) Other contributing factors to cognitive impairment such as uncontrolled hypothyroidism (TSH >10 mU/l) or untreated low vitamin B12 (<250 ng/mL);
- (7) Uncontrolled congestive heart failure reflected by poor exercise tolerance and shortness of breath at rest or with some exertion;
- (8) Actively undergoing chemotherapy or radiation therapy for cancer treatment;
- (9) History of stroke in the past 3 years;

- (10) Severely impaired cognition (MoCA ≤10, FAST >5 or CDR >2);
- (11) Inability to have MRI and LP e.g. for MRI, metal implants or cardiac pacemaker or for LP, bleeding diathesis from disease states or from use of anticoagulants such as warfarin, heparin and related products, Rivaroxaban or Xarelto, Apixaban or Eliquis, Edoxaban or Savaysa, Dabigatran or Pradaxa. Subjects who can have either one LP or MRI will be enrolled;
- (12) Inability to have cognitive assessment due to hearing, vision, or language issues or due to severe impairment;
- (13) History of increased intracranial pressure (ICP);
- (14) In those who are unable to demonstrate that they understood the details of the study using the UBACC modified for EMERALD (i.e. lack of decisional-capacity to consent), a study partner/surrogate who can sign on their behalf will be required; otherwise, they will be excluded;
- (15) Use of phenobarbital or rifampin due to drug interaction.

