7. SAFETY ASSESSMENTS

7.1. SPECIFICATION OF SAFETY PARAMETERS

(i) The following safety parameters are related to the use of Montelukast: The finding of an elevated ALT, AST, or bilirubin ($> 3 \times \text{ULN}$) or other clinical evidence of liver disease such as jaundice, encephalopathy. Headache, stomach cramps, fever, nasal congestion, upper respiratory tract infection and throat irritation are less common side effects.

Other infrequent side effects of Montelukast include runny nose, diarrhea, dizziness, fatigue, joint or muscle pain, bronchitis, gastroenteritis, pancreatitis, rash, dental pain, and ear or skin disorders. Angioedema, eosinophilia, vasculitis, increased bleeding tendencies, seizures, altered behavior and suicidal thoughts are also rare but potential complications of Montelukast.

(ii) The following safety parameters are related to the conduct of the study procedures: Neuropsychological assessment may be accompanied by anxiety, frustration and overall fatigue. The attachment and removal of a blood pressure cuff, cuffs for venous occlusion, and ultrasound probe on the neck may cause mild discomfort. Brain imaging requires the participant to stay still and lie down for 50-70 minutes, which may cause boredom and minimal reversible back pain. Because of the closed space and noise, undergoing an MRI may be associated with anxiety or panic reactions. The vascular ultrasound is safe and only mildly uncomfortable due to discomfort in the arm when the cuff is inflated. We will use ultrasound to painlessly bounce sound beams off the carotid artery using a pencil-like sensor.

(iii) The following safety parameters are related to the LP procedure: The most common complication of a lumbar puncture is post-LP headache. We use a smaller 24-gauge Sprotte spinal needle. All subjects will be counseled on the signs and symptoms of post-LP headaches and given information on management (acetaminophen, caffeine, rest). Bacterial meningitis and a CSF leak are very rare complications of lumbar punctures. A blood patch is rarely needed to heal CSF leaks. All subjects will be instructed to promptly contact us if the headache persists beyond 3 days and if a blood patch is required, the cost of the patch will be covered by the funds supporting this project.

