7.4. FOLLOW-UP FOR ADVERSE EVENTS

All AE/SAE will be recorded in the participant chart with start/stop date. The study physician may perform additional evaluations, unscheduled visits, phone communication, repeat blood testing, or refer to the emergency room or the participant healthcare provider for medical care if necessary. If the event results in intervention discontinuation (>5 months) but not study withdrawal, the participant will be followed as defined in the study. They will also be invited to perform the final visit evaluation including all study procedures planned for that visit if the participant has been in the study for more than 5 months post-baseline evaluation.

When a subject notifies the study team that they have symptoms suggestive of a treatment-emergent AE/SAE, the study physician will review the incident and determine if the subject is safe to continue in the study. The physician may discontinue the study medication immediately, elect to lower the dose of the study medication, ask subject to present to the study center for a safety evaluation, and/or monitor the subject's concern. The subject may continue in the study if on the lower dose of the study medication, they experience some resolution of symptoms. In those on 20 mg and 40 mg, the doses will be decreased to the next lower dose. In those on 10 mg of Montelukast, a trial of every other day 10 mg of Montelukast will be attempted prior to discontinuation.

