8. INTERVENTION DISCONTINUATION AND STUDY WITHDRAWAL

A subject may choose to withdraw from the study for any reason. Also, the investigators may also request that a subject withdraw from the study or intervention be discontinued, for safety or other reasons. The criteria for intervention discontinuation or study withdrawal may include:

- (1) The subject's request;
- (2) Inability to participate due to relocation or other personal reasons;
- (3) Adverse events that require un-blinding or necessitate stopping the study drugs;
- (4) Seizures;
- (5) Persistent increase in elevated liver enzymes following study dose de-escalation or clinical or biochemical evidence of hepatic disease.

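### Section 5.1's liver rule is tied to 3 times baseline only, so a participant who enters above 1 × ULN can pass the 3 × ULN signal of 7.1 with no mandatory step-down or triggered 2-week recheck

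*Combined protocol and SAP*

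**What the plan says.** - **Section 5.1** starts everyone on 10 mg and raises the dose at 2-week steps to 20 and 40 mg, provided symptoms are tolerable and "liver enzymes checked at 6 weeks do not exceed 3X baseline levels". If that limit is passed, "dose will be decreased to the prior level (20 mg or matched placebo) and LFT rechecked 2 weeks later". Further steps to 10 mg and then to stopping follow if the values do not settle. This is the only numeric liver rule in the protocol that makes action obligatory.
- **Section 7.1** opens its list of Montelukast-related parameters with "The finding of an elevated ALT, AST, or bilirubin" above 3 × ULN, "or other clinical evidence of liver disease such as jaundice, encephalopathy". No dose step or retest is attached.
- **Section 4.2, item 3**, excludes "Liver disease (elevated liver enzymes" more than twice normal). It covers ALT, AST, alkaline phosphatase and total bilirubin. Values between 1 and 2 × normal are admissible.
- **Section 8** lists grounds for stopping under the words "The criteria for intervention discontinuation or study withdrawal may include". Item 5 is "Persistent increase in elevated liver enzymes following study dose de-escalation or clinical or biochemical evidence of hepatic disease".
- **Section 7.4** says of a participant who reports symptoms: "The physician may discontinue the study medication immediately, elect to lower the dose of the study medication", among other options.
- **Table 1** schedules liver tests at screening and then at 6 weeks and 3, 6 and 12 months. The screening panel is the only one before dosing.

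**The concern.** The protocol uses two scales for the same hazard. The obligatory rule is relative to the participant's own starting value; the named drug signal is absolute. Where the starting value is at or below the upper limit of normal, the relative rule is at least as strict and nothing is lost. Where it is above, the relative rule becomes the looser of the two, and the people given the most room are those who entered with the highest values.

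The result is an odd ordering. Someone who goes from 0.5 to 1.6 × ULN must step down and be retested in 2 weeks. Someone who goes from 2.0 to 5.9 × ULN need not be. At stake is the safety of the few participants admitted with raised values. With 2-week steps from 10 mg, 40 mg is reached at about week 4, so they would normally be on the top dose when the week-6 panel is drawn. Safety is part of the primary objective, and raised liver enzymes are a listed safety outcome in Table 2.

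**Working it through.** The plan states no figure to reproduce; this is a comparison of thresholds.

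**Inputs.** 5.1 trigger: more than 3 × baseline at 6 weeks. 7.1 signal: more than 3 × ULN. Entry limit in 4.2(3): 2 × normal. Panels: 6 weeks and month 3 (Table 1). Visit windows: ±1 week at week 6, ±3 weeks otherwise (6.10.2). Planned enrolment: 36, allocated 1:1 (sections 3 and 5.1).

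**Assumptions.** Normal in 4.2(3) means ULN. Baseline means the screening panel. 5.1 is taken to cover bilirubin, because 4.2(3) counts bilirubin among the liver enzymes.

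**Step 1: put both rules on the ULN scale.** With baseline b × ULN, 5.1 acts above 3b × ULN and 7.1 flags values above 3 × ULN. A value above 3 and up to 3b × ULN meets 7.1 but not 5.1. That band exists only if 3b > 3, that is, b > 1. The rise needed to reach 3 × ULN is 3/b.

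| b (× ULN) | 5.1 acts above (3b) | Uncovered band (× ULN) | Rise to reach 3 × ULN (3/b) |
|---|---|---|---|
| 0.5 | 1.5 | none | 6.0-fold |
| 0.75 | 2.25 | none | 4.0-fold |
| 1.0 | 3.0 | none | 3.0-fold |
| 1.25 | 3.75 | 3.0 to 3.75 | 2.4-fold |
| 1.5 | 4.5 | 3.0 to 4.5 | 2.0-fold |
| 2.0 | 6.0 | 3.0 to 6.0 | 1.5-fold |

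Section 5.1 also describes the trigger as a 3x increase. If that meant baseline plus three times baseline (4b), the gap would open at b > 0.75 and reach 8 × ULN at b = 2. The explicit limit of 3 times baseline makes 3b the natural reading, and it is used here.

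**Step 2: time to the next required liver test.** Month 3 is 3 × 52/12 = 13 weeks.
- Nominal: 13 − 6 = 7 weeks.
- Shortest with windows: (13 − 3) − (6 + 1) = 3 weeks.
- Longest with windows: (13 + 3) − (6 − 1) = 11 weeks.
- Under 5.1 when triggered: 2 weeks.

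**Step 3: how many people.** The documents give no distribution of entry liver values. With assumed shares of 2%, 5% and 10% entering above 1 × ULN:
- Total: 36 × 0.02 = 0.7; 36 × 0.05 = 1.8; 36 × 0.10 = 3.6.
- On Montelukast (half): about 0.4, 0.9 and 1.8.

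Only those whose week-6 value then falls inside the band are affected, which is fewer still.

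**Step 4: do other sections oblige action in the band?**
- 7.4 starts from symptoms the participant reports, which a silent enzyme rise does not produce. Its repeat testing and dose changes are options for the physician.
- 8(5) has one limb that presupposes a dose reduction has already happened. The other could cover a value above 3 × ULN but has no number, and the whole list is permissive.
- 7.2 and 7.3 require rating of adverse events and an assessment for reporting. 7.5 requires telling the participant about incidental findings, or referral if urgent.

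None of these makes a dose cut or an early retest obligatory.

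**The case against.** The strongest reply has four parts.

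**Section 7.1 is a watch list, not a dosing rule.** It sets liver values beside headache and nasal congestion and attaches no dose action to any of them. That is correct. A reader might infer that 5.1 and 7.1 contradict each other; they do not. The point is only that the protocol's own liver signal can be passed without its obligatory liver action.

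**Physicians already have the means to act.** A value above 3 × ULN can be read as biochemical evidence of hepatic disease under 8(5), which permits stopping outright. 7.4 allows repeat blood tests and dose reduction, and says doses of 20 or 40 mg go down one level, though in the setting of a symptom report. Exclusion 5 adds a judgement on safety at entry. Most physicians would probably act. This limits the seriousness but does not close the gap: 5.1 does not leave a threefold rise to discretion, and the documents give no reason to treat a value above 3 × ULN differently.

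**A baseline-relative limit suits people who start high.** It avoids reacting to an elevation already present, and extra dose cuts have a price in a trial that also studies dose-response. This is a fair design argument, and the choice may be deliberate. The protocol does not make that argument, however, and 7.1 applies its limit with no exception for raised baselines.

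**The numbers are tiny.** This stands. The 6 × ULN ceiling applies only at b = 2.0, and the 11-week wait needs both visits at opposite ends of their windows.

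**Conclusion.** The gap is real and small. For entry values above 1 and up to 2 × ULN, a week-6 result above 3 and up to 3b × ULN (at most 6 × ULN) requires neither a step-down nor a triggered 2-week recheck. The next required panel comes about 7 weeks later. The number affected is probably zero to one or two; that rests on assumed shares, since the documents are silent. The finding also depends on reading normal as ULN and the screening panel as baseline.

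Stronger readings that the documents do not support:
- *That no liver recheck is required.* Everyone has a liver panel at month 3; only the triggered 2-week recheck is absent.
- *That participants in general are under-protected.* Below 1 × ULN, 5.1 is stricter than 7.1.
- *That the delay extends to the 3- and 6-month intervals after later visits.* 5.1 names only the 6-week check, so its reach at later panels is unclear rather than shown to fail.
- *That the treatment comparison is biased.* The rule is the same in both arms and is applied blind.

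This is an improvement worth considering, not an error that threatens the trial.

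**What to change.** In 5.1, make the existing step-down and 2-week recheck apply when ALT, AST or bilirubin exceeds 3 × ULN **or** liver enzymes exceed 3 × baseline. Refer to this trigger in 7.1 and 8(5). The limit then becomes the smaller of 3b and 3 × ULN, so the uncovered band is empty for every admissible entry value: at b = 2.0 the trigger falls from 6 to 3 × ULN, at b = 1.5 from 4.5 to 3. Keeping the baseline limb means nothing is loosened for those who start low.

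As a separate clarification, which the week-6 gap does not itself require, state that the same trigger applies at the month-3 and month-6 panels, with only the recheck at month 12, when treatment ends.

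The cost is a wording amendment and no new scheduled blood draws. The downside is a few more blinded dose reductions and unscheduled rechecks in both arms, mainly among those entering with raised values; at b = 2.0 a rise of just over 1.5-fold would trigger.

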5.2. HANDLING OF STUDY INTERVENTIONS

The drugs will be stored in the medication room in the Investigational Drug Service (IDS) Pharmacy. The primary location of the IDS pharmacy is The Emory Clinic [name]. This location will serve the satellite Emory IDS pharmacy used for this study, at the Executive Park campus. Access to the med room is limited to the IDS Pharmacists via a badge swipe. Accountability records are maintained for all investigational product (IP). A courier will deliver prescriptions to study location to be given to subjects or study staff will be able to pick up prescriptions.

5.3. CONCOMITANT INTERVENTION

5.3.1. ALLOWED INTERVENTIONS

Participants will continue to receive their usual care from their regular primary care physicians. In the event that during the trial period, a participant is required to be on a LTRA (Montelukast or other similar agents), the prescribing physician and the subject will be informed they might be receiving Montelukast to avoid any overlap. If an alternative treatment is prescribed that is safe to be used with Montelukast, then they can continue on the study medications. Participants who start on a LTRA (or a drug that potentially lead to contraindication for using LTRA) clinically will have their study medication discontinued but will continue to be in the study and have their subsequent visits and measures completed.

5.3.2. PROHIBITED INTERVENTIONS

Participation in another clinical trial or study is prohibited.

5.4. ADHERENCE ASSESSMENT

Participants will be asked to bring their study medication bottles to the study center at each visit. Medication compliance will be assessed using pill count during the follow up periods. We will define a compliance rate for a time period, t, as the ratio of: ((the used number of pill prescribed for the number of days t - number of pills remaining or unused for the time t)/ number of pills prescribed for time t) multiplied by 100.

6. STUDY PROCEDURES AND MEASURES

6.1. QUESTIONNAIRES, LIFESTYLE AND ANTHROPOMETRIC MEASURES

Study interviews will be conducted in English and include the following:

(1) Demographic, social, stress, physical activity using the Physical Activity Scale for the Elderly (PASE),^{35,36} and medical history data, as well as a medication inventory will be collected. All participants are asked to bring all their prescribed medication bottles.

(2) Functional Activities Questionnaire (FAQ),³⁷ Functional Assessment Staging Tool (FAST),³⁸ and Instrumental activities of daily living (IADL) scale.³⁹

(3) Weight and height (stadiometer to measure height with the subjects standing and balance beam scale to measure weight without shoes).

(4) Short Physical Performance Battery (SPPB): ability to stand with the feet side-by-side, semi-tandem, and tandem, time to walk 8 feet (measured twice), and time to rise from a chair and return to the seated position 5 times.⁴⁰

(5) Additional questionnaires will be collected at various visits including The University of California, San Diego Brief Assessment of Capacity to Consent (UBACC),⁴¹ NIH Toolbox Perceived Stress and Hostility,^{42,43} Race and Ethnicity Scale (RES), and Everyday discrimination scale (EDS).⁴⁴

6.2. BLOOD PRESSURE MEASUREMENT

Office blood pressure will be measured according to the American Heart Association guidelines⁴⁵- sitting position, rested for 5 minutes, appropriate cuff size (covering 60% of upper arm length and 80% of arm circumference), correct cuff placement (1-2 inches above brachial pulse on bare arm). Measurement will be done manually using the bell of the stethoscope or using a validated and calibrated automatic machine. Blood pressure will be measured in both arms. The arm with the higher blood pressure will be used throughout the study. We will obtain 2 seated blood pressure measurements 5 minutes apart, followed by 2 standing readings at 1 and 3 minutes during each visit.

6.3. NEUROPSYCHOLOGICAL ASSESSMENT:

(i) *Clinical Dementia Rating (CDR)*: The CDR rates each of the six general domains (or boxes) involving memory, orientation, judgment and problem-solving, community affairs, home and hobbies, and personal care, and a global rating is then generated, ranging from 0-no impairment to 3-severe impairment. A study informant or study partner will be questioned either by phone or in person to assist with the CDR.

(ii) *NIH Toolbox Cognition Battery (NIHTB-CB)*: (www.nihtoolbox.org)⁴⁶: This is a computer-based test battery that reliably and validly assesses neurocognitive sub-domains in clinical trials, including working memory, episodic memory, processing speed, language, attention and executive function.⁴⁷ The NIHTB-CB has excellent psychometric properties with test-retest reliability up to 0.92, and correlates ($r=0.78-0.90$) with Gold Standard Fluid, Crystallized and Total cognitive composites measuring everyday executive functioning.⁴⁸⁻⁵⁰ Parts of the NIH Toolbox that we selected include:

- 1) Flanker Inhibitory Control and Attention test assesses attention and executive function and involves the allocation of one's limited capacities to deal with an abundance of environmental stimuli.⁵¹
- 2) Picture Sequence Memory test, a measure of episodic memory assessing cognitive processes involved in the acquisition, storage and retrieval of new information.⁵²
- 3) List Sorting Working Memory test assesses working memory.⁴⁷
- 4) Picture Vocabulary test assesses language by measuring receptive vocabulary.⁵³
- 5) Pattern Comparison Processing Speed test assesses processing speed, the amount of information that can be processed within a certain unit of time.⁵⁴
- 6) Dimensional Change Card Sort Test, a test of executive function, will assess cognitive flexibility and the capacity to plan and organize.⁵¹

(iii) To assess additional cognitive domains/mood, we will use these tests, some of which are included in the National Alzheimer's Coordinating Center Uniform Data Set.^{55,56}

- 1) Verbal Fluency will be tested using a List Generation test which require the participant to generate words beginning with a specific letter, and category fluency in which the participant generates words from a specified category (e.g., animals, fruits).⁵⁷
- 2) Hopkins Verbal Learning Test will be used to assess memory domains.⁵⁸
- 3) Digit Span Test (DST) is a brief task that assesses attention.^{59,60}
- 4) Boston Naming Test assesses language by measuring ability of naming a visual confrontation drawing (15 items).^{61,62}
- 5) Trail Making Test will be used as an additional measure of executive function.⁶³

6) Center for Epidemiologic Studies Depression Scale (CESD),⁶⁴ consists of 20 items, each scored from 0 to 3 points and higher scores indicate greater depressive symptoms.

7) Sheehan Suicidality Tracking Scale (S-STS), a sensitive psychometric tool to prospectively monitor for treatment-emergent suicidal ideation and behaviors in AD clinical trials.^{65,66}

8) Neuropsychiatric Inventory Questionnaire (NPI-Q), a concise assessment of behavioral changes in patients with AD or other dementias.⁶⁷⁻⁶⁹

9) Montreal Cognitive Assessment (MoCA), a brief screening test for cognitive impairment in older adults.^{70,71}

(iv) Voice recording to assess speech changes related to cognitive function may be collected at one or more visits. These will include a recording of the cognitive tests, free speech, speech in response to questions, and speech in response to specific cognitive tasks such as counting, fluency and/or a picture description. All voice recording files will not contain personal identifiers or PHI. They will be saved under the subject deidentified study number.

